1.1 Disease Background

Non-Hodgkin Lymphoma (NHL) is ranked as the 5th to 9th most common cancer in most countries worldwide, with almost 510,000 new cases estimated in 2018 ([Miranda-Filho, 2019](#)). Follicular lymphoma (FL) represents the 2nd most common subtype of NHL and ~20–25% of all new NHL diagnoses in western countries ([Carbone, 2019](#)). In the United States (US), the annual incidence of FL was 2.7 per 100,000 on 2017 ([Howlader N, 2020](#)). In Western Europe, the annual incidence of FL has rapidly increased during recent decades and has risen from 2–3/100,000 during the 1950s to 5/100,000 recently ([Mounier M, 2015](#)). While the majority of patients with FL will respond to initial therapy, almost all of them will relapse; thus, FL is considered incurable ([Hiddeman, 2014](#)) and is an area of significant unmet medical need.

Currently approved therapies for relapsed/refractory (R/R) FL include lenalidomide combined with rituximab and obinutuzumab combined with bendamustine, both of which have full approval in second line, and the phosphatidylinositol 3-kinase (PI3K) inhibitors (idelalisib, copanlisib, and duvelisib), all of which have accelerated approval in third line in US. Idelalisib is only PI3K inhibitor received accelerated approval by Europe Medicines Agency (EMA). In addition, the enhancer of zeste homolog 2 (EZH2) inhibitor tazemetostat received US Food and Drug Administration (FDA) accelerated approval for adult patients with R/R FL whose tumors are positive for an EZH2 mutation and who have received at least 2 prior systemic therapies, and for adult patients with R/R FL who have no satisfactory alternative treatment options. Standard first-line therapy uses immuno-chemotherapy. Although current front-line regimens for Stages III and IV FL such as CHOP (cyclophosphamide, doxorubicin, vincristine, prednisone) plus obinutuzumab or rituximab, or bendamustine plus obinutuzumab or rituximab are associated with high response rates, most patients still relapse. The approved second line therapies have overall response rates (ORRs) ranging from 59% to 80%, with complete response rates (CRRs) ranging from 16% to 46% ([Gazyva® US- Prescribing Information; Revlimid® US-Prescribing Information; Andorsky 2019; Leonard 2019](#)). The approved PI3K inhibitors have ORRs ranging from 42% to 59%, with substantially lower CRRs of 1% to 14% ([Zydelig® US- Prescribing Information; Aliqopa™ US- Prescribing Information; Copiktra® US- Prescribing Information](#)). The approved EZH2 inhibitor tazemetostat has ORR 69% with CRR 12% for patients with EZH2 mutant, and ORR 34% with CRR 4% for patients with EZH2 wild-type ([TAZVERIK™ US- Prescribing Information](#)). There are a number of agents available for second-line therapy, including cytarabine-containing regimens and idelalisib. It has been reported idelalisib is effective in patients with high-risk FL and early relapse after initial immune-chemotherapy, with 56.8% ORR, 13.5% CRR, and 11.8 months duration of response (DOR) ([Gopal et al., 2017](#)).

However, FL is characterized by successive lines of therapy resulting in progressively shorter periods of disease-free survival followed ultimately by the development of either chemotherapy refractoriness, large cell transformation, or death from treatment-related

toxicities (Cheah, 2018). Thus, there remains unmet medical needs for novel drugs for patients with R/R FL.

[figure not shown]
1.2 Description of the Study Drugs

1.2.1 Loncastuximab tesirine (ADCT-402)

Loncastuximab tesirine (ADCT-402) is an antibody drug conjugate (ADC), composed of a humanized monoclonal antibody (RB4v1.2) directed against human cluster of differentiation 19 (CD19) conjugated through a cathepsin-cleavable linker to SG3199, a pyrrolobenzodiazepine (PBD) dimer cytotoxin. The toxin SG3199 attached to the linker is designated as SG3249.

The schematic representation of loncastuximab tesirine is presented in [Figure 1](#).

Figure 1. Schematic Representation and Chemical Structure of Loncastuximab Tesirine

Abbreviations: Ala=alanine; HC=heavy chain; LC=light chain; PABA=para-aminobenzoic acid; PBD=Pyrrolobenzodiazepine; PEG=polyethylene glycol; RB4v1.2=human monoclonal antibody being studied; Val=valine.

Loncastuximab tesirine binds with picomolar affinity to human CD19. After binding and internalization, loncastuximab tesirine traffics to the lysosomes, where the protease-sensitive linker is cleaved and unconjugated PBD dimers (SG3199) are released inside the target cell. The released PBD dimers bind in the minor groove of DNA and form potent cytotoxic DNA

interstream cross-links. The cross-links result in a stalled DNA replication fork, blocking cell division and causing cell death ([Hartley, 2011](#)). The cross-links formed by PBD dimers are relatively non-distorting to the DNA structure, making them hidden to repair mechanisms ([Adair et al, 2017; Beck et al, 2017](#)).

More detailed information about loncastuximab tesirine may be found in the Investigator's brochure ([Loncastuximab tesirine IB](#)).

1.2.2 Idelalisib

Idelalisib is a small molecule, an inhibitor of PI3K. Idelalisib induced apoptosis and inhibited proliferation in cell lines derived from malignant B-cells and in primary tumor cells. Idelalisib inhibits several cell signaling pathways, including B-cell receptor signaling and the CXCR4 and CXCR5 signaling, which are involved in trafficking and homing of B-cells to the lymph nodes and bone marrow. Treatment of lymphoma cells with idelalisib resulted in inhibition of chemotaxis and adhesion, and reduced cell viability.

More detailed information about idelalisib may be found in the idelalisib prescribing information or Summary of Product Characteristics ([Idelalisib® US- Prescribing Information; Idelalisib-SmPC](#)).

1.2.3 Clinical Study Data for Loncastuximab Tesirine and Idelalisib

Loncastuximab tesirine

ADCT-402-101 (NCT02669017, <https://clinicaltrials.gov/ct2/show/NCT02669017>), was a first-in-human Phase 1 dose-escalation study of loncastuximab tesirine in R/R B-cell NHL patients. The data from this study showed loncastuximab tesirine exhibits significant anti-tumor activity in heavily pretreated patients with R/R FL, with an ORR of 78.6% and a CRR of 64.3%. Median duration of response and median progression free survival (PFS) were both not reached.

Toxicity was manageable, with the most common Grade ≥ 3 treatment-emergent adverse events (TEAEs) being Gamma-glutamyl transferase (GGT) increased (21.3%); neutropenia (16.9%); anemia (15.3%); neutrophil count decreased (14.8%); thrombocytopenia (12.0%); platelet count decreased (10.4%); blood alkaline phosphatase (ALP) increased (6.6%); lymphocyte count decreased (6.6%); disease progression (6.0%); febrile neutropenia (5.5%); and hypokalemia (5.5%) ([Loncastuximab tesirine IB](#))

Idelalisib

Idelalisib is the only PI3K inhibitor approved by FDA and EMA as monotherapy for the treatment of adult patients with FL that is R/R to two prior lines of treatment.

In Study 101-09 (NCT01282424, <https://clinicaltrials.gov/ct2/show/NCT01282424>), 72 patients with FL received 150 mg of idelalisib orally twice (BID) daily until evidence of disease progression or unacceptable toxicity. The ORR was 55.6% and CRR was 16.7%. The median PFS was 11.0 months (range 8.0–14.0), and the median DOR was 11.8 months (range 6.2–26.9) ([Idelalisib -SmPC](#)).

The most common Grade ≥ 3 TEAEs in 125 adults with indolent non-Hodgkin lymphoma treated with idelalisib 150 mg BID in clinical trials were elevated transaminases (21%), diarrhea (13%), neutropenia (27%), pneumonia (7%), and thrombocytopenia (6%) (Gopal et al, 2014).

1.3 Benefit/Risk Assessment

The primary benefit for this study is that of effective treatment for lymphoma, although this benefit is not guaranteed. The primary risk of this study is the toxicities from the treatment; for loncastuximab tesirine, the most common adverse reactions are gamma-glutamyl transferase increased, neutropenia, thrombocytopenia, fatigue, anemia, nausea, cough, edema, and blood ALP increased, and for idelalisib the most common adverse reactions are diarrhea, fatigue, nausea, cough, pyrexia, abdominal pain, pneumonia, and rash and the most common laboratory abnormalities are neutropenia, alanine aminotransferase (ALT) elevations, and aspartate aminotransferase (AST) elevations. It is expected that the potential benefit of effective treatment will outweigh the potential toxicities, providing a positive risk/benefit ratio.

2 Study Rationale

Non-Hodgkin Lymphoma is ranked as the 5th to 9th most common cancer in most countries worldwide, with almost 510,000 new cases estimated in 2018. Follicular lymphoma represents the 2nd most common subtype of NHL and ~20–25% of all new NHL diagnoses in western countries. While the majority of patients with FL will respond to initial therapy, almost all of them will relapse; thus, FL is considered incurable and is an area of significant unmet medical need.

Loncastuximab tesirine (ADCT-402) is an antibody drug conjugate (ADC) that has been designed to target and kill CD19-expressing malignant B-cells. CD19 is highly expressed in B-cell NHL, including follicular lymphoma. Data from a Phase 1 study of loncastuximab tesirine in relapsed or refractory B-cell NHL showed significant activity of loncastuximab tesirine in heavily pretreated patients with relapsed/refractory follicular lymphoma, with an ORR of 78.6% and a CRR of 64.3%. Median DOR and median PFS were both not reached. Data from loncastuximab tesirine studies demonstrated an acceptable safety profile to date and a positive risk-benefit for further evaluation in R/R FL.

2.1 Rationale for Study Design

This is a Phase 2, randomized, 2-arm, and open-label study and will enroll approximately 150 patients. Eligible patients will be randomly assigned to treatment with loncastuximab tesirine or idelalisib in a 2:1 ratio. The randomization will be stratified based on time since last systemic therapy (\leq 2 years vs >2 years). A randomized trial design was chosen as this is a well-recognized standard for evaluating new treatments. The study is an open label trial as the primary endpoint is tumor response as determined by central review, which is unlikely to be affected by investigator or subject knowledge of treatment assignment. The sample size is driven by a regulatory agency request to have safety data on ~100 FL patients treated with loncastuximab tesirine. With 100 patients treated in the loncastuximab tesirine arm and complete response rate as the primary endpoint, the study would be substantially overpowered with a standard 1:1 randomization scheme, so a 2:1 randomization is used to limit the number of patients required to complete the study, which still results in a power of $>99\%$.

Idelalisib was chosen as the comparator for this study as it is the only PI3K inhibitor currently approved for treatment of R/R FL in both the US and Europe.

2.2 Rationale for Dose Selection

Loncastuximab tesirine will be administered intravenously (IV) at a dose of 150 $\mu\text{g}/\text{kg}$ every 3 weeks for 2 doses, then at a dose of 75 $\mu\text{g}/\text{kg}$ every 3 weeks at the subsequent doses.

The initial dose of 150 $\mu\text{g}/\text{kg}$ every 3 weeks (Q3W) was based on the observation that response rate in patients treated in the Phase 1 trial appeared to increase with increasing exposure, but toxicity was substantially increased at 200 $\mu\text{g}/\text{kg}$ compared to lower dose levels. Thus, 150 $\mu\text{g}/\text{kg}$ was chosen as the highest initial dose with acceptable toxicity. The dose reduction after 2 cycles was based on the fact that a substantial portion of patients treated on the Phase 1 trial required dose reduction after 2 or more cycles, usually as a result of prolonged dose delays

because of adverse events (AEs). Decreasing the dose after 2 cycles was intended to reduce the incidence of dose delay and reduce the need for further dose reduction. This dosing regimen has been used in 145 patients in a Phase 2 study of loncastuximab tesirine in patients with R/R diffuse large B-cell lymphoma (R/R DLBCL) and appears to be well-tolerated with a manageable toxicity profile and comparable efficacy to that achieved in a similar patient population in Phase 1.

3 Study Objectives and Endpoints

Table 3. Study Objectives and Endpoints

Objectives	Endpoints
Primary	
To evaluate the efficacy of single agent loncastuximab tesirine compared to idelalisib in patients with relapsed or refractory follicular lymphoma.	Complete response rate (CRR) according to the 2014 Lugano classification as determined by central review in patients with FL. Complete response rate is the proportion of patients with a best overall response (BOR) of complete response (CR) assessed prior to any subsequent anticancer treatment.
Secondary	
To further evaluate the additional efficacy of single agent loncastuximab tesirine compared to idelalisib in patients with relapsed or refractory follicular lymphoma.	
Key Secondary Endpoint
 
Overall response rate (ORR) defined as the percentage of patients with a BOR of CR or partial response (PR) by central review assessed prior to any subsequent anticancer treatment. 
Other Secondary Endpoints
 
Progression free survival (PFS) defined as the time between the randomization date and the first documentation of recurrence, progression, or death.Overall survival (OS) defined as the time between the randomization date and death from any cause.Duration of response (DOR) defined as the time from the documentation of tumor response to disease progression or death.
To assess the safety profile of loncastuximab tesirine in patients with relapsed or refractory follicular lymphoma.	
Incidence and severity of adverse events (AEs) and serious adverse events (SAEs).Changes from baseline of safety laboratory values, vital signs, 12-lead electrocardiogram (ECG), and Eastern Cooperative Oncology Group (ECOG) performance status.

Objectives	Endpoints
To characterize the pharmacokinetics (PK) profile of loncastuximab tesirine.	Concentrations and PK parameters of loncastuximab tesirine total antibody, pyrrolobenzodiazepine (PBD)-conjugated antibody, and unconjugated warhead SG3199.
To evaluate the immunogenicity of loncastuximab tesirine.	Anti-drug antibody (ADA) titers
To evaluate the impact of loncastuximab tesirine treatment compared to idelalisib on patients-reported outcomes (PROs) (eg, symptoms, functions, and overall health status).	
Change from baseline in PROs as measured by EuroQol-5 Dimensions-5 Levels (EQ-5D-5L) and Functional Assessment of Cancer Therapy - Lymphoma (FACT-Lym)The occurrence, severity, and interference of specific symptomatic adverse events selected from Patient-Reported Outcomes version of the Common Terminology Criteria for Adverse Events (PRO-CTCAE™)
[REDACTED]	[REDACTED]

4 Study Design

4.1 Overview

This is a prospective, randomized, 2-arm, multi-center, and open-label Phase 2 study in patients with R/R FL. The study will enroll approximately 150 patients. Eligible patients will be randomly assigned to treatment with loncastuximab tesirine or idelalisib in a 2:1 ratio. A block randomization with stratification based on time since last systemic therapy (≤ 2 years vs >2 years) will be used. A non-binding futility analysis on the primary endpoint of CRR will be performed for the first 60 patients around 12 weeks after the 60th patient is randomized (enough time for 2 disease assessments). The duration of the study participation for each patient is defined as the time from the date of signed written informed consent to the completion of the follow-up period, withdrawal of consent, loss to follow-up, or death, whichever occurs first.

The study will include a screening period (up to 28 days), a treatment period (cycles of 3 weeks for loncastuximab tesirine treatment and cycles of 4 weeks for idelalisib treatment), and a follow-up period (approximately every 12 weeks visits) for up to 3 years from treatment discontinuation ([Section 4.2](#), study periods).

4.2 Study Periods

4.2.1 Screening Period

Informed consent must be obtained for each patient and documented with a signed informed consent form (ICF) prior to any study procedures. Procedures that are performed as part of SOC may be used to satisfy screening requirements if they are performed in the appropriate window.

The screening period is from 28 days to 1 day prior to the start of the study drug. The screening assessments should be performed within this period in order to assess the eligibility of the patient against the inclusion and exclusion criteria ([Sections 5.1](#) and [5.2](#), respectively).

See [Section 5.3](#) for the information to be collected on screening failures.

4.2.2 Randomization

Patients who are eligible will be randomized via Interactive Response Technology (see Interactive Response Technology manual for details). The randomization will be stratified based on time since last systemic therapy (≤ 2 years vs >2 years). Block randomization with size of 3 will be used to generate the randomization list. Approximately 150 patients will be randomized (2:1 ratio) to receive either loncastuximab tesirine or idelalisib. For details on randomization steps and for treatment assignment, see [Section 6.3](#).

4.2.3 Treatment Period

The treatment period will start on the date when a patient is administered the first dose of study treatment and continues until the end of treatment (EOT) visit (see below).

A treatment cycle is defined as 3 weeks (i.e., 21 days) for patients assigned to loncastuximab tesirine treatment. A treatment cycle is defined as 4 weeks (i.e., 28 days) for patients assigned to idelalisib treatment. Patients will receive either IV loncastuximab tesirine on Day 1 of each cycle, or idelalisib 150 mg BID orally Days 1-28 every cycle. Patients may continue treatment until disease progression, unacceptable toxicity, death, or other discontinuation criteria, whichever occurs first.

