Abbreviations: ADA: anti-drug antibody; AE: adverse events; BP: blood pressure; β -HCG: β subunit of Human chorionic gonadotropin; C: cycle; C1D1: cycle 1 day 1; [REDACTED] CMV: cytomegalovirus; CT: computerized tomography; ECG: electrocardiogram; ECOG: Eastern Cooperative Oncology Group; EOI: end of infusion; EOT: end of treatment; FACT-Lym: The Functional Assessment of Cancer Treatment-Lymphoma questionnaire; FDG: (18)F-fluorodeoxyglucose; [REDACTED]; HBV: hepatitis B virus; HCV: hepatitis C virus; HIV: human immunodeficiency virus; HR: heart rate; ICF: informed consent form; IV: Intravenous; MRI: Magnetic resonance imaging; PCR: polymerase chain reaction; PK: pharmacokinetics; PRO-CTCAE: Patient-Reported Outcomes Version of the Common Terminology Criteria for Adverse Events; RR: respiratory rate; SAE: serious AEs; Temp: temperature;.

Visit Scheduling Windows:

- Treatment Period: Visit day \pm 3 days (excluding C1D1 which is the reference day).
- EOT: As soon as possible after decision to discontinue the study treatment but preferably at least 30 days after last dose of study treatment unless a new anticancer treatment is planned to be administered before the 30 days, in which case EOT should be conducted before initiation of the new anticancer treatment.
- Follow-up Period: Visit day \pm 14 days.

²Vitals should be taken at pre-dose and EOI for every loncastuximab tesirine dosing visit.

³Positron-emission tomography-computed tomography will be used to perform imaging study. If disease is not FDG-avid at baseline, CT or MRI may be used. Screening imaging must be performed within 4 weeks prior to C1D1 and the same assessment method must be used throughout the study. Week 6 and Week 12 imaging should be performed within \pm 5 days of the scheduled timepoint. All other imaging for disease assessment should be performed within \pm 2 weeks of the

scheduled time point. Imaging for disease assessment should be performed at the scheduled timepoint even if drug dosing is delayed. Additional disease assessments may be obtained, if clinically indicated.

⁴During follow-up period disease assessments to be performed in patients who discontinued study treatment for reasons other than disease progression or initiation of other anti-cancer therapy (except for hematopoietic stem cell transplant).

⁵ \leq 3days prior to administration of study treatment for loncastuximab tesirine arm patients.

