6.7 Dose Delays and Modifications

6.7.1 Dose Delays and Modifications for Loncastuximab Tesirine and Idelalisib

The criteria and guidance for dose delay and dose modifications of loncastuximab tesirine and idelalisib are summarized in [Table 4](#) and [Table 5](#), respectively.

Table 4. Criteria for Dose Delay or Dose Modification of Loncastuximab Tesirine

Toxicity	Loncastuximab Tesirine
Grade ≥ 3 non-hematologic adverse events	
Hold until the toxicity resolves to Grade ≤ 1, (Grade 1 or baseline for peripheral neuropathy)If dosing is delayed by more than 3 weeks and the toxicity is considered at least possibly related to loncastuximab tesirine, then subsequent doses must be reduced by 50%. If the toxicity recurs, subsequent doses must be reduced by an additional 50%A maximum of 2 dose reductions are allowedNote: Patients who have a toxicity meeting the criteria for dose reduction following Cycle 2 will receive the protocol-specified dose of 75 $\mu\text{g}/\text{kg}$ for Cycle 3, i.e., they will not have an additional dose reduction for Cycle 3
Grade ≥ 2 edema, effusion	
Hold until the toxicity resolves to Grade ≤ 1If dosing is delayed by more than 3 weeks and the toxicity is considered at least possibly related to loncastuximab tesirine, then subsequent doses must be reduced by 50%. If the toxicity recurs, subsequent doses must be reduced by an additional 50%A maximum of 2 dose reductions are allowedNote: Patients who have a toxicity meeting the criteria for dose reduction following Cycle 2 will receive the protocol-specified dose of 75 $\mu\text{g}/\text{kg}$ for Cycle 3, i.e., they will not have an additional dose reduction for Cycle 3

Toxicity	Loncastuximab Tesirine
Grade ≥ 3 neutropenia or thrombocytopenia	
• Hold until toxicity resolves to Grade ≤ 2• If dosing is delayed by more than 3 weeks and the toxicity is considered at least possibly related to loncastuximab tesirine, then subsequent doses must be reduced by 50%. If the toxicity recurs, subsequent doses must be reduced by an additional 50%• A maximum of 2 dose reductions are allowed• Note: Patients who have a toxicity meeting the criteria for dose reduction following Cycle 2 will receive the protocol-specified dose of 75 $\mu\text{g}/\text{kg}$ for Cycle 3, i.e., they will not have an additional dose reduction for Cycle 3

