9.11 PROs Data Analyses

Patient-reported outcomes will be analyzed using PRO population. Completion rate of each PRO questionnaire (completed questionnaires as a proportion of the expected) will be calculated. Item level missing values will be imputed as per recommendation by the instrument developers.

Changes from baseline (Cycle 1 Day 1) in PRO scores for physical well-being, LymS subscale, FACT-G total, TOI, and FACT-Lym total of FACT-Lym, as well as EQ-5D VAS will be estimated at each cycle for each treatment arm. The changes from baseline in these scores will be compared between the two treatment arms. Patients will be classified as improvement/deterioration based on the established minimally important differences for each measure. Proportion of patients with improvement/deterioration as well as time to improvement/deterioration will be estimated for each treatment arm and compared between the two treatment arms.

The occurrence, severity, and interference (per relevance) of specific symptomatic adverse events selected from PRO-CTCAE, as well as the proportion of patients reporting 'quite a bit' or 'very much' in GP5 item of FACT-Lym will be presented at approximately 3 months and 6 months for each treatment arm, and compared between the two treatment arms.

Full details will be further described in the SAP.

10 Regulatory, Ethical, and Study Oversight/Management Considerations

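### FACT-Lym and EQ-5D-5L scores are to be summarised by cycle, but a cycle is 21 days and moves with dose holds in one arm and is 28 days in the other

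*Combined protocol and SAP*

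**What the plan says.** Cycle lengths differ (Section 4.2.3): "A treatment cycle is defined as 3 weeks (i.e., 21 days) for patients assigned to loncastuximab tesirine treatment", and "A treatment cycle is defined as 4 weeks (i.e., 28 days) for patients assigned to idelalisib treatment". The same section ties Day 1 to the infusion in one arm and to continuous tablets in the other: "Patients will receive either IV loncastuximab tesirine on Day 1 of each cycle, or idelalisib 150 mg BID orally Days 1-28 every cycle".

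Tables 1 and 2 place FACT-Lym (to Cycle 18 in both arms) and EQ-5D-5L on Day 1 of each cycle. PRO-CTCAE and GP5 are answered on C1D1 and then at home on Day 10, to Cycle 9 on loncastuximab tesirine and Cycle 7 on idelalisib.

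For qualifying toxicities Table 4 (Section 6.7.1) holds loncastuximab tesirine: "Hold until the toxicity resolves to Grade" 1 or less, or 2 or less for neutropenia and thrombocytopenia. Long holds are foreseen: "If dosing is delayed by more than 3 weeks and the toxicity is considered at least possibly related to loncastuximab tesirine", the dose is reduced. Table 5 also withholds idelalisib for toxicity, without saying what happens to the cycle days.

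For imaging, footnote 3 of Tables 1 and 2 says: "Imaging for disease assessment should be performed at the scheduled timepoint even if drug dosing is delayed". Nothing equivalent is written for the questionnaires.

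Section 7.6 has FACT-Lym and on-treatment EQ-5D-5L completed at the site, electronically, and before clinical assessment where applicable. Section 9.11 says that the FACT-Lym scores, "as well as EQ-5D VAS will be estimated at each cycle for each treatment arm", and then compares changes, proportions improving or deteriorating, and times to these events between arms. PRO-CTCAE and GP5 are compared at about 3 and 6 months.

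**The concern.** Comparing patient-reported outcomes between arms is a stated secondary objective of an open-label trial. Two features of the schedule put the arms on different clocks.

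First, a by-cycle comparison sets different amounts of elapsed time side by side. Second, when an infusion is held, the Day 1 forms of later cycles move with it, and the next one falls when the patient has recovered enough to be dosed. Scores from the middle of the hold are not scheduled, so no later analysis can recover them. The plan guards imaging against this but not the questionnaires.

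At stake are the mean changes, the proportions deteriorating and the times to deterioration on FACT-Lym and EQ-5D.

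**Working it through.** **1. Does a hold move the loncastuximab tesirine cycle?** No sentence says so directly, but the note in Table 4 implies it. Nominal Day 1 is week 3 × (k − 1): Cycle 3 at week 6, Cycle 4 at week 9. Dose reduction requires a delay of more than 3 weeks, so a patient who meets that criterion after Cycle 2 is next infused later than week 6 + 3 = 9. On a fixed calendar that dose would belong to Cycle 4 or later. The note still calls it Cycle 3, so the cycle number follows the infusion. Pre-dose and end-of-infusion PK samples on Day 1 of Cycles 1 to 6 (Table 6) agree with this.

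**2. Timing by cycle with no holds.** Loncastuximab tesirine Day 1 is week 3 × (k − 1); idelalisib Day 1 is week 4 × (k − 1).

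| Cycle k | Loncastuximab tesirine | Idelalisib | Gap (weeks) |
|---|---|---|---|
| 2 | week 3 | week 4 | 1 |
| 5 | week 12 | week 16 | 4 |
| 9 | week 24 | week 32 | 8 |
| 18 | week 51 | week 68 | 17 |

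By week 24 the planned post-baseline Day 1 forms number 24/3 = 8 against 24/4 = 6.

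**3. Effect of a hold on Day 1 forms.** A 3-week hold before Cycle 9 moves its Day 1 from week 24 to week 27 for that patient. The gap to idelalisib at that cycle number falls from 8 to 5 weeks, but one cycle number now covers several elapsed times within the arm. If the hold is decided before the visit, or the form is not repeated at re-dosing, the interval between forms is 21 + 21 = 42 days. If a form is completed both at the scheduled visit and at re-dosing, each interval is 21 days, but two forms compete for one cycle number and Section 9.11 does not say which counts.

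**4. PRO-CTCAE and GP5.** Study day = cycle length × (cycle − 1) + 10.
- About 3 months: 21 × 4 + 10 = 94 and 28 × 3 + 10 = 94.
- About 6 months: 21 × 8 + 10 = 178 and 28 × 6 + 10 = 178.

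The plan's 3- and 6-month times are therefore reproduced and match across arms. A 3-week hold moves the loncastuximab tesirine forms to days 115 and 199.

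**5. Possible size.** The documents give no hold rate and no score loss. One simulation used the same toxicity process in both arms. Its assumptions are onset 0.02 to 0.04 per week, mean duration 2 to 4 weeks, a score 10 points lower during an episode with full recovery, every episode present on a scheduled Day 1 leading to a hold, and idelalisib forms on the calendar. The loncastuximab tesirine form is completed on the scheduled Day 1 and the hold starts afterwards. By week 24:
- patients with at least one form showing the fall: about 22% to 48% on loncastuximab tesirine and 19% to 45% on idelalisib;
- artificial mean difference: about 0.03 to 0.46 points towards loncastuximab tesirine.

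The two summaries point in opposite directions. The mean favours loncastuximab tesirine, because the rest of the hold is under-recorded. The proportion with any recorded fall is slightly higher on loncastuximab tesirine; its more frequent forms give more chances to catch one.

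**The case against.** The best reply is that Section 7.6 puts questionnaires before clinical assessment. A patient who arrives for a scheduled Day 1 with toxicity would normally fill in the form and then be held, so the fall is on record. This largely stands. The exception is a hold decided before the visit, for example on laboratory results drawn up to 3 days earlier.

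A reader might go further and infer that questionnaire coverage switches off during toxicity in one arm only. Simulating that reading gives 0% of loncastuximab tesirine patients with a recorded fall against 18% to 46% on idelalisib, and a mean artefact of 0.4 to 1.3 points. The documents do not support it. The 0% comes from postponing every form due during toxicity, which Section 7.6 contradicts.

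Other parts of the reply also stand:
- Idelalisib forms continuing on the calendar while drug is withheld is inferred from continuous Days 1–28 dosing; it is not stated.
- After C1D1, PRO-CTCAE and GP5 fall about 10 days after re-dosing, not at recovery. No direction of bias can be claimed for them.
- Many holds may be for laboratory findings that need not lower a score. GGT increase and cytopenias lead the Grade 3 or higher events in Section 1.2.3.
- Section 2.2 says Phase 1 dose reductions were "usually as a result of prolonged dose delays", but the step-down regimen used here was meant to reduce delays.
- Section 9.11 leaves full details to the SAP, which could set a different time axis. No SAP text in the document does so.

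The reply does not answer the unequal cycle lengths, which need no assumption about holds, or the absence of a dose-delay rule for the questionnaires.

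**Conclusion.** The point holds as a liability to bias, not as a demonstrated one-arm bias. Two parts rest on the protocol: the same cycle number means different times in the two arms (8 weeks apart at Cycle 9, 17 at Cycle 18), and a hold delays later loncastuximab tesirine Day 1 forms without any form scheduled during the rest of the hold.

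The direction is probably modestly towards loncastuximab tesirine for mean Day 1 scores, provided idelalisib forms stay on the calendar and the held toxicities lower the score. It need not be the same for the proportion deteriorating. The 0.03 to 0.46 points illustrate assumed rates and an assumed 10-point fall; they are not an estimate for this trial.

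These endpoints lie outside the CRR-then-ORR test sequence, so the primary conclusion is unaffected. The change is still worth making because scores not collected during a hold cannot be recovered.

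**What to change.** 1. **Section 9.11:** compare FACT-Lym and EQ-5D scores, including the proportion with and time to deterioration, by time since C1D1 or randomization in common windows, not by cycle number. The nominal schedules coincide every 12 weeks: weeks 12, 24, 36 and 48 are Day 1 of Cycles 5, 9, 13 and 17 on loncastuximab tesirine and of Cycles 4, 7, 10 and 13 on idelalisib. State which form counts if two fall in one window.
2. **Tables 1 and 2 and Section 7.6:** state for both arms that FACT-Lym and EQ-5D-5L are completed at the nominal time from C1D1 even if dosing is delayed or withheld, and allow remote electronic completion during a hold.
3. **PRO-CTCAE and GP5:** leave them on Day 10, so that they keep their relation to the infusion, but assign them to the 3- and 6-month comparisons by actual date.

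The cost is a few extra electronic forms for patients on hold, a reminder keyed to C1D1, and a relaxation of the on-site rule in Section 7.6. Some forms would then be completed away from the site, so the place of completion should be recorded. No extra visits are needed.
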